9.2 Risk of Contrast Agent

This study does not intend to use MRI or CT contrast agents.

9.3 Risks incidental to the MRgFUS treatment

- There is a potential risk of conscious sedation, which includes reaction to the drugs or over-sedation.
- There is a potential risk from the intravenous catheter used during the treatment. Subjects can expect a small amount of pain and/or bleeding/bruising at the IV site. There is a small risk of infection. This procedure will follow the ‘standard of care’ at the Study Sites.
- There is a potential risk to the subject of deep venous thrombosis from lying stationary for 3 to 4 hours. The risk to the subject from lying still for this treatment should be no greater than that of lying still for any other reason. Subjects will be provided compression stockings, as described above (Section 4.3), to use during treatment. All subjects will be screened for DVT prior and post-ablation procedure. This will further reduce the risk to subjects by screening out all those with DVT risk prior to ablation.
- There is a risk that the subject may experience a sore neck or discomfort from lying in the same position for a long time during the treatment.
- There is a potential risk from a urinary catheter if used during the procedure. Participant may expect varying levels of Urinary Tract Infection due to the use of the urinary catheter. In a different study for the MRgFUS treatment of uterine fibroid (Pivotal study under IDE G020001 that lead to PMA approval under PMA # P040003), the incidence of this risk was found not to exceed 3.7%. This procedure will follow the “standard of care” at the study sites.

9.4 Risks Associated with the MRgFUS Treatment

- There is a potential risk of hemorrhage during MRgFUS treatment. In MRgFUS thermal ablation, the high temperature at the focal point results in immediate protein denaturation and coagulative necrosis. This should be expected to rapidly stop any bleeding that might occur in the capillary bed and within small vessels. At the end of the MRgFUS procedure an unenhanced MR scan is performed to assess the treated area and adjacent tissues.
- There is a risk of discomfort to the subject caused by heating of tissue. Focused ultrasound therapy involves precisely controlled pulses of thermal energy resulting in tissue coagulation (typically 55-65°C for several seconds) in small tissue volumes. This induces thermal coagulation of the targeted soft tissue. The energy intensity at the level

of the skin is quite low, and there should be no local heating, hence no sensation of pain at the scalp. The rise in temperature in the skull should be kept to below pain level by active cooling of the water within the rubber diaphragm. Because the focal point of the beam will be > 2.5 cm from the dura and there are no pain receptors in the brain, there should be no pain associated with ablation. The subject will be in verbal contact with the physician and appropriate action can be taken in the event that a subject does experience discomfort. Remedies could involve lowering energy levels, increasing the time interval between consecutive treatment pulses, or increasing the level of sedation and/or analgesia. The subject also has the ability to abort the sonication at any time by activating a handheld cut off circuit (i.e., stop switch).

- There is a risk of imprecise targeting of the focal point, and ablation of an area of tissue outside the planned treatment volume. If this occurred it is possible that serious neurological deficit or even death could result. To limit the risk of this occurring, the treatment process includes a mandatory verification step that requires the operator to first check the alignment of the subject anatomy, the focal point of the transducer and the MR imaging system. This procedure, done while the subject is in position for treatment, uses a very low energy sonication to confirm of the alignment of the focal point and the targeted treatment point in all three axes. For each sonication delivered during treatment, the operator gets continuous feedback on the position of the intended treatment point superimposed on the thermal dosimetry image and can make corrections where required. At any point in the treatment process this low-power verification of the localization may be repeated prior to full power sonication.
- There is the risk that the tissue along the path to the target (scalp, skull, dura, brain, etc) could become heated to the point where tissue-damage or a burn might occur. This heating could be caused by direct improper treatment targeting, irregularities on the skin surface (e.g.: scars), treatment of a volume of tissue too close to the skin or bone, energy absorption by the bone, or the conduction of sufficient heat to cause a burn at the surface. In the case of a first or second degree burn of the scalp, the skin should heal without a scar. In the case of a 3° burn, a scar, or loss of sensation in the area of the burn could result.
- Although skin burn is a risk associated with both the ExAblate Neuro and body systems, there have been no cases of skin burn in all ExAblate Neuro treatments; over 400 subjects have been treated with the ExAblate Neuro system to date. However, over the last decade, there have been four reports of skin burns in breast treatments and two reports of skin burns in uterine fibroid treatments. These subjects were treated with the ExAblate body system. The circumstances of these events are not applicable to the ExAblate Neuro system. However, the heating in the energy pass zone is always monitored and an additional cooling time can be administered when elevated temperatures are detected. Because the issue of energy absorption and overheating of the skull and scalp is so critical in the brain application, this system includes an active cooling sub-system that circulates the water in the space between the face of the transducer and the scalp. This will help keep the scalp within a safe temperature range and reduce the risk of overheating. If non-superficial tissue along the path to the target

were to become heated to the point that damage occurs, there is the possibility that it would result in significant neurological damage or even death. To reduce the possibility that this could occur, several measures will be taken:

- First, the procedure is performed in the MR scanner. During the treatment MR images will be acquired. Using specific scanning sequences and a rapid post-processing program, changes in temperature can be detected, and a thermal map of the brain generated. This thermal map will reveal any potentially dangerous elevations in temperature.
- Third, MR-compatible pulse oximeter, blood pressure cuff, and EKG monitor will be monitored throughout the procedure. This information will permit detection of tissue damage, edema, or bleeding, if brain or blood vessels along the beam paths are injured by heat.
- Finally, the subject and the neurosurgeon will each have a stop switch that can instantaneously interrupt the energy delivery at any time. The subject is given a stop switch in case aberrant tissue heating causes any compromise to speech, word finding, or other communication difficulties. The subject will be instructed prior to the proceeding that they should use the stop switch any time they feel excessive pain, discomfort, disorientation or any other unusual sensation. The neurosurgeon has a stop switch so that if there is any sign of neurological change, the energy delivery can be immediately stopped and the subject carefully evaluated. Temporary interruption of energy delivery will in no way compromise the potential for therapeutic benefit to the subject. Following subject evaluation treatment can resume without delay.

- There is a risk associated with subject motion during a sonication or between sonifications. This could cause a movement of the tissue relative to the planned treatment volume on the system, and in extreme cases could result in the treatment of a point outside the planned treatment volume. Also, because the skull functions as a defocusing lens, the phase correction map computed for the target spot will become ineffective if the subject moves. To prevent or minimize this risk, there are several precautions taken to prevent motion, and to detect it, if it occurs:
 - The system is equipped with a movement detection algorithm. Prior to each sonication, a brief MRI assessment is made of fiducials in the transducer. If any of the fiducials are misaligned within the voxel coordinate system of the MRI, the system will not proceed. The movement detection algorithm is set to trigger with alterations of >2mm.
 - During subject positioning every effort will be made to make the subject comfortable and the subject will be educated as to the importance of maintaining their position during the treatment.
 - The subject will be managed with conscious sedation. This will enable them remain still during the procedure.

- The subject will be placed in a head immobilization unit based on a stereotactic frame. This technology has been effective in preventing movement in stereotactic neurosurgery, and has been adapted and modified to the specification of MR-guided FUS.
- One or more members of the medical team will be in the room throughout the sonication to monitor the subjects' medical status and comfort. Hence, subject motion will also be monitored.
- There is a risk of cavitation in the tissue at the focal point. Cavitation is the collapse of rapidly developed gas bubbles at the focal point due an extreme intensity of ultrasound excitation. This rapid collapse could cause high pressure, shock waves, and high temperatures. All systems are now equipped with cavitation detectors.
- There is a risk of blood brain barrier (BBB) disruption, edema, swelling, hemorrhage outside and remote to the targeted area. These events may theoretically occur due to heating effects (ie secondary hot spots) and or to the pressure wave of the ultrasound beam. The secondary hot spots risks are discussed below. To address the risks due to pressure waves of the ultrasound beam path, the system has been designed to be well below the "pressure wave threshold" that may trigger events of this nature. In all cases, thermal and regular imaging will be continuously assessed during the procedure. Finally, the subject(s) is continuously monitored by the anaesthesiologist (or nurse anaesthetist) during the ablation procedure for any change in the subject condition.

9.5 Risks related to bilateral lesioning of central lateral thalamic nucleus

We perceive the following primary risks of bilateral FUS medial thalamotomy based on our review of the historical literature of medial thalamotomy, the extensive experience of CL thalamotomy by our colleague Jeanmonod, and our experience with FUS Vim thalamotomy for ET:

1. Somatosensory deficit & increase pain – from lateral extension of the lesion to VPL
2. Transient cognitive disturbance or confusion
3. Hemorrhagic morbidity – from thermal ablation
4. Cavitation – from focused ultrasound

Somatosensory deficit & increased pain.

Medial thalamic lesions target the intralaminar nuclei and do not result in discriminative somatosensory deficits. Historical lesion of the lateral thalamus (VPM/VPL) often resulted in somatosensory deficits and increased pain due to deafferentation. In order to mitigate this risk, medial thalamic lesions will be confined to the CL nucleus and will not extend laterally to the VPM. The laterality of the coordinates for medial thalamic lesions will be maintained less than 10 mm.

The thermal lesioning process with focused ultrasound could cause **neurological effects** for several reasons. Any effects outside of the treatment area could result in neurologic signs or symptoms. These could occur from the thermal lesioning process that is 'off-target' or

associated infarction, hemorrhage or edema. Subjects will be observed and monitored during the treatment for signs of neurologic side effects. They will also be observed overnight on the neurosurgical ward. Most neurologic side effects would manifest within minutes to hours. Those related to cerebral edema will be transient and expected to resolve within 2-3 weeks.

Perioperative confusion has infrequently been observed with medial thalamotomy procedures. Jeanmonod reported one case of somnolence from 96 Radio Frequency (RF) CL thalamotomies¹⁰⁰ and no occurrences when the lesions performed with FUS.⁵⁴ The risk of this almost certainly increases with older age. In order to mitigate the risks of perioperative confusion or cognitive decline, subjects will undergo preoperative psychological assessment to gauge their cognitive reserve exclude those with significant cognitive impairment. The precise delivery of acoustic energy with MR-guidance will ensure that lesions are not delivered outside of the targeted CL nuclei – a technology that much less susceptible to confounding features like brain shift or stereotactic inaccuracies. MRgFUS has been shown consistently with submillimeter precision.^{79,81}

Symptomatic intracerebral hemorrhage with stereotactic procedures has been consistently estimated to range from 1 to 2%, and may be slightly higher with pallidotomy procedures which have been reported in large series to almost 4%. Intracerebral hemorrhage from stereotactic RF lesions likely occurs in a slightly higher fashion than stereotactic FUS lesioning because electrode penetration of the brain is required. In order to mitigate the risk for intracerebral bleeding from FUS, subjects with severe hypertension and coagulopathy will be excluded from trial participation, and normotension will be maintained throughout all procedures.

In the RF ablation experience of the PI, out of a series of 94 radiofrequency lesioning procedures for movement disorders, a single 10-mm thalamic hemorrhage was noted in a subject undergoing thalamotomy at a probe tip temperature of 70°C. (unpublished data) It is difficult to translate the probe tip temperature in an RF lesion to the target volume temperature of an MRgFUS lesion, but it may be postulated that thermal lesioning at higher temperatures could increase the risks of hemorrhage. In order to minimize such risk, we propose to perform permanent ultrasound lesioning bilaterally with a measured temperature of 65°C at the target. This temperature is sufficient for thermal coagulation of the target but well below the peak temperature observed in the case cited above. The experience of the ExAblate TcMRgFUS thalamotomy in the treatment of subjects with neuropathic pain and Essential tremor entailed treatment to 65°C at target without any observed neurologic or hemorrhagic consequences.

Cavitation. More recently, Jeanmonod et al. achieved central lateral thalamotomy ablations with submillimeter precision⁷⁹ for therapy resistant neuropathic pain syndromes using focused ultrasound. There was a single thalamic hemorrhage resulting in neurologic morbidity which possibly occurred from cavitary effects. This complication led to the universal adoption of cavitation detectors in the ExAblate technology.⁵⁴

Delayed ischemic infarction has been rarely observed with stereotactic RF lesioning of the basal ganglia. The occurrence of this complication has been only reported in 3 of 50 cases of RF pallidotomy, and these cases occurred in subjects with a significant history of vasculopathy

identified either clinically or radiographically.¹⁰¹ These ischemic events occurred in a delayed fashion at 10, 51, and 117 days following the procedure. One of 89 subjects undergoing subthalamotomy presented with a delayed onset of involuntary movements at one week and imaging suggested a thalamic/subthalamic infarction¹⁰² It is postulated that these delayed infarctions results from damage to the perforating of vessels of the basal ganglia. Lenticulostriate perforating vessels are much less prevalent in the medial thalamus. Subjects at risk for bleeding (low clotting factors or anticoagulants) are excluded. In addition, heating should seal vessels.

Infection has been rarely observed with stereotactic lesioning and certainly with less frequency than occurs with implanted devices from DBS procedures. We anticipate a negligible risk for meningitis or brain abscess with ExAblate thalamotomy as this is not an open brain procedure requiring incisions or burr holes through the skull.

Mortality. There have been no mortalities in over 400 ExAblate Neuro ablations performed worldwide. The mortality rate with surgical radiofrequency thalamotomy, a much more common procedure that has been employed for decades, has not been reported and likely occurs in much less than 1% of cases. At the University of Virginia, over 100 radiofrequency thalamotomies have been performed without mortality.

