9.0 RISK MITIGATION

Worldwide, over 12,500 treatments have been performed to date with the MR guided FUS ExAblate body system. Risk analysis for InSightec ExAblate systems/clinical investigations has been conducted as part of previously approved FDA IDE submissions (G930140, G990151, G990184, G990201, G000203, G010225, G020001, G020182, G050177, and G060023, G070022, G080009, G080206). This data has been re-examined by InSightec and it has been concluded that this risk analysis has limited applicability to the proposed clinical investigation. The key consideration here is the fact that this proposed study is conducted with an ExAblate Neuro that is completely different from the body system. This system is referred to internally as the Exablate Neuro system. However, in principle, the body and brain systems have the same purpose namely to coagulate soft tissue within the body by means of MR guided high intensity focused ultrasound. The potential risks described below will be explained to the subject in the informed consent process.

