9.8 Anticipated Treatment Side Effects from MRgFUS

All adverse events will be reported in the Case Report Forms (CRFs) and analyzed for their relation to the ExAblate device as well as other causes (Expected procedure findings, Drug/Contrast media reactions, Medical conditions, and Unrelated to device or procedure). Adverse events related to the device or procedure occur during or shortly after the procedure (within 30 days) since the effect is a one-time, focal treatment. Based on existing treatment experience in the brain using the ExAblate Neuro Type 1.0 (650 KHz), the following anticipated side effects have been identified as possibly occurring during/following the ExAblate procedure.

9.8.1 Procedure-related events include:

- Claustrophobia. Medications may be useful in controlling symptoms, but may also result in nausea/vomiting.
- Pain/discomfort:
 - Sonication-related headache or head/face flushing or warmth. Usually these are transient, but are coincident with a sonication. Headache may occasionally last for several days.
 - Headache may relate to the headframe or fasting status. The brain has no pain sensors, but the scalp, dura and bone tissues do.
 - Position-related pain related to being uncomfortable in the scanner (e.g., sore neck, back pain, muscle or joint pain).
- Hypertension/hypotension, and bradycardia/tachycardia may be related to pre-procedure nervousness or comorbid conditions / missed medication dose pre-procedure as an NPO requirement. Medications can be administered peri-procedure to control them.
- Neurological deficits may result from damage to nearby structures in the brain and thus is specifically related to the target location. To date, the following has been reported:
 - vestibular with or without vegetative manifestations
 - paresthesias
 - dysesthesias/pain.

9.8.2 Events which are Unrelated to the ExAblate device include:

- Events associated with the headframe, such as pin site pain, pin site or scalp/facial edema, pin site burning or bleeding.
- Events associated with the urinary catheter, such as urinary tract infection.

- Events associated with the intravenous line used to administer medications, such as infection and/or bruising.
- Events that are associated with comorbid conditions or unforeseen circumstances.

9.8.3 Drug reactions include:

- Nausea or vomiting
- Dizziness
- Overdose or mis-dosing in error

9.8.4 Events related to malfunction or mis-use of the device include:

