Feasibility Study for Neuropathic Pain Outside the US - ExAblate 4000 Type-1 Neuro System An investigator initiated and sponsored study in the treatment of neuropathic pain was conducted at the University Hospital Zurich (Zurich Switzerland) using the InSightec ExAblate Neuro (650 KHz) system. The study was approved by and performed according to the guidelines of the ethics committee of the University and the State of Zurich. Nineteen (19) subjects with chronic, medication-resistant neuropathic pain underwent selective central lateral thalamotomy (CLT) using the ExAblate Neuro treatment. Therapy-resistance was defined as occurring when the subject's pain was not effectively treated with medication.	Feasibility Study for Essential Tremor IDE - G100169 - ExAblate 4000 Type-1 InSightec received FDA approval for a feasibility trial of ExAblate Neuro System for unilateral thalamotomy in the treatment of Essential Tremor under IDE # G100169. Total of 15 subjects were enrolled and treated at one site. This study has been completed and the full results of this study were published in the New England Journal of Medicine . ¹⁰⁶ Based on the investigator and the subject's feedback, subjects have shown a great level of acceptance of the procedure. Furthermore, subjects have shown a significant improvement in their Essential Tremor disease following their unilateral treatment with the ExAblate Neuro device. Subjects who completed the study requirements have shown stability of the tremor suppression all the way to the end of the study.
--	--

For all subjects, the treatment was well tolerated and did not result in any side effects or neurological deficits. The only significant event reported to date from this study is an event of neurological deficit, i.e. “dysmetria (dyscoordination) of the right hand, dysarthria, motor neglect and gait disorder”. This event was reported immediately following the last sonication.

All subjects experienced some level of pain relief during the procedure, and at 48 hours after the treatment, subjects reported pain relief ranging from 30 to 100% (mean = 68%).⁸⁰ Partial results of this study were published in the *Annals of Neurology Journal*.⁵⁴

**Feasibility Study for Essential Tremor
ITA# 166556- ExAblate 4000 Type-1**

A similar feasibility study in 6 subjects was also conducted at Sunnybrook, Toronto under Health Canada Application # 166556 and published in *Neurotherapeutics*.¹⁰⁷

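### Section 9.5 supports 65°C with a no-harm statement that the protocol's own reports contradict, leaves out the below-60°C precaution taken after a bleed, and the peak-voxel target has two lower bounds

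*Protocol*

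**What the plan says.** **Justification of 65°C.** Section 9.5 of the Protocol proposes permanent bilateral lesions at a measured 65°C and gives two reasons. The first is that 65°C is enough to coagulate tissue and lies below the 70°C probe temperature of one radiofrequency case that bled. The second is that focused ultrasound experience in neuropathic pain and essential tremor "entailed treatment to 65°C at target without any observed neurologic or hemorrhagic consequences".

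**Reported harm.** Section 2.8 and the cavitation paragraph of 9.5 each describe one thalamic bleed with neurologic injury in the neuropathic-pain series and name cavitation detectors as the response. The abstract in Appendix A reports the same complication, gives peak temperatures of 51 to 64°C in 11 treated patients, and names two responses: a cavitation detector and keeping sonication under 60°C.

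Section 9.8 builds its list of anticipated effects as follows: "Based on existing treatment experience in the brain using the ExAblate Neuro Type 1.0 (650 KHz". Under 9.8.1, neurological deficits are described as "specifically related to the target location. To date, the following has been reported", followed by vestibular effects, paresthesias, and dysesthesias or pain.

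Appendix B describes the closed neuropathic-pain study of 19 subjects, done "using the InSightec ExAblate Neuro (650 KHz) system". It says: "For all subjects, the treatment was well tolerated and did not result in any side effects or neurological deficits". The next sentence reads: "The only significant event reported to date from this study is an event of neurological deficit", and the components include dysmetria "of the right hand, dysarthria, motor neglect and gait disorder".

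**Temperature targets.** Steps 18b and 19d of section 6.5, section 9.5 and the closing paragraph of 9.8 each give a temperature for the lesion. They are set side by side in the working.

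**The concern.** A statement that earlier treatment caused no neurologic or haemorrhagic harm carries weight when it is used to support a temperature. Here the same section, two other sections and both appendices report such harm. The paragraph that makes the statement also postulates that hotter lesions could bleed more, so the temperature precaution taken after the bleed is directly relevant there. It is missing from the body of the protocol.

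Three things are at stake.

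- **Consent.** Section 9.0 says: "The potential risks described below will be explained to the subject in the informed consent process". An incorrect reassurance in section 9 can therefore reach subjects.
- **Safety assessment.** Safety is the primary outcome and the lesions are permanent and bilateral. Under section 10.0, whether a device effect is unanticipated depends on what the plan has already identified, and under 10.1 the DSMB asks whether an event was unexpected. Prior harm should be stated correctly for those judgements.
- **Conduct.** An operator who reads 6.5 and 9.8 together finds two different lower limits for an adequate lesion.

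**Working it through.** The plan gives no figure to reproduce: it has 10 subjects and proposes no statistical analysis. The check compares statements.

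**1. The no-harm sentence against the reports of harm**

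- Section 9.5 claims 0 neurologic or haemorrhagic consequences in neuropathic pain and essential tremor.
- Section 2.8, the cavitation paragraph of 9.5 and Appendix A report 1 bleed, in neuropathic pain.
- Appendix B reports 1 neurological deficit, in neuropathic pain. It may be the same event, so the two are not added.
- Section 9.8.1 lists 3 kinds of deficit already reported. That list covers brain experience with the 650 kHz system generally and is not tied to pain and tremor alone, so it is supporting evidence only.

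The count is therefore at least 1, not 0.

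The sentence might have been meant to cover only sessions that reached 65°C. It sets no such limit and gives no number of sessions. The appended paper could not support that reading: its peaks lie 65 − 64 = 1°C to 65 − 51 = 14°C below 65°C.

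**2. Related statements**

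Appendix B denies any deficit in any subject and reports one in the next sentence. The 9.8.1 list does not name dysmetria, dysarthria or motor neglect, although Appendix B reports them from the same 650 kHz system.

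**3. Measures taken after the bleed**

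Appendix A names 2. Sections 2.8 and 9.5 carry over 1 of 2, and the one left out concerns temperature.

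**4. Temperature wording**

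| Place | Value | Measure |
|---|---|---|
| 6.5, step 18b | 60–65°C | peak voxel |
| 6.5, step 19d | up to 60°C | over a 5 mm zone |
| 9.5 | 65°C | at the target |
| 9.8, closing paragraph | 55–65°C | peak voxel |

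Step 18b and 9.8 use the same measure for the same study lesion.

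- Lower bound: 60 − 55 = 5°C apart.
- Upper bound: 65 − 65 = 0°C apart.

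A side that ended at a 57°C peak would meet 9.8 and fail 18b. Step 19d uses a different measure, so its 60°C is not counted as a contradiction of 18b. The text does not say whether it caps escalation under 18b.

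**5. Reach**

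Assume an even split (5 active), crossover of all 5 sham subjects, and both sides treated. Then (5 + 5) × 2 = 20 lesions at most, subject to the early stops in steps 19d and 20.

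No event rate by temperature is derived. The temperature at the bleed is not given, and 9.5 attributes the bleed only possibly to cavitation.

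**The case against.** The strongest reply is that nothing is hidden. The paragraphs that follow in 9.5 report the bleed, that section lists haemorrhage and cavitation among its four primary risks, and 9.8 lists bleeding, infarction and death as possible. The sentence speaks of treatment to 65°C, so a bleed in a series that peaked at 64°C does not strictly refute it. Other sessions may have reached 65°C: Appendix B counts 19 subjects against 11 in the paper, and tremor treatments are included. Section 9.0 promises to explain risks, which need not include this reassurance, and the consent text is not available. The below-60°C measure was another group's precaution, is printed in Appendix A, and may refer to a different temperature measure. The like-for-like mismatch is only in the lower bound, which does not raise bleeding risk.

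Much of this is fair and limits the point. The bleed is disclosed, the precaution does not bind this study, the 65°C top value is consistent, and steps 18b and 19d may be compatible. That the sentence reaches subjects is possible but not shown.

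The reply does not rescue the sentence. The narrow reading is not in the text, and on that reading the appended series gives 65°C no support. Disclosure in 9.5 is also incomplete, because it presents the bleed as possibly cavitary, answers it with detectors, and leaves out the measure that bears on temperature. The Appendix B wording can be read as a rule followed by its exception, but as written the first sentence is false.

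**Conclusion.** The point holds and should be fixed. The main error is the 9.5 sentence, which claims no consequences where the protocol reports at least 1 haemorrhage with neurologic morbidity. The supporting errors are the self-contradiction in Appendix B, the incomplete list in 9.8.1, 1 of 2 post-bleed measures missing from the body, and a 5°C conflict in the lower bound of the peak-voxel target with step 19d left unreconciled.

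This rests on the plain reading of the sentence and on the appended abstract. It does not assume that 65°C is unsafe, that temperature caused the bleed, or that the bleed and the Appendix B deficit are separate events. The first reason given for 65°C is not disputed. With cavitation detection, stop buttons, stopping rules and DSMB review in place, this calls for a correction and is no reason to halt the study.

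**What to change.** - **9.5:** report the haemorrhage, the neurological deficit and the 51 to 64°C peaks in the appended paper. If a statement about 65°C sessions is kept, give their number and outcomes.
- **9.8.1 and Appendix B:** add the Appendix B deficit to the list, and correct the Appendix B sentence that denies any deficit.
- **2.8 and 9.5:** name the below-60°C measure beside the cavitation detector, and give the reason this study goes above it.
- **6.5:** state one peak-voxel target and ceiling, and say how the 5 mm, 60°C criterion relates to them. Align 9.5 and 9.8 with it.

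Whether to lower the limit below 60°C is a clinical decision for the sponsor, the investigator and the DSMB and is not part of this fix.

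The cost is an amendment to the risk text and a clarification in 6.5. Sample size, visits and treatment limits stay as they are. The downside is a less favourable risk statement, and any consent text that repeats the 9.5 sentence would need the same correction.
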